# 10.4 Assessment of efficacy parameters before using the rescue medication

In this study, patients with unbearable pain are allowed to use the rescue medication no earlier than 2 hours after administration of the investigational drug. For such patients, it is necessary to carry out the following procedures:

- Before using the rescue medication, dispensing questionnaires to the patient to record the following:
  - o Pain intensity in the assessed joint according to VAS;
  - o Patient global assessment of the efficacy using a categorical scale;
- Registering the time of use of the rescue medication and enter the results in the source documentation and CRF.

#### 10.5 Unscheduled visits

Patients can ask the investigator to appoint an unscheduled visit at any time if they have adverse events, or if their condition requires medical intervention. The investigator may schedule an unscheduled visit to the patient to assess the safety of the therapy.

To register an unscheduled visit, the Investigator shall enter obtained data in the source medical documents and the CRF ('Unscheduled Visit' page). The Investigator will have to make sure to record the following information: the date of the visit, the reasons for it, and the data obtained as a result of physical examination and additional tests conducted.

After an unscheduled visit, the next visit should be conducted as planned, in accordance with the Study Protocol.

## 11 DESCRIPTION OF THE VARIABLES AND ASSESSMENT METHODS

#### 11.1 Baseline characteristics

# 11.1.1 Information on the primary disease

The CRF should contain the following characteristics of the underlying condition:

- The original diagnosis of the primary condition and the date of diagnosis;
- Date of diagnosis of acute gout attack;
- Count of joints affected by gout:
  - o 1 joint affected (acute monoarticular gout)
  - o 2 to 4 joints affected (acute oligoarticular gout)
  - o 5 or more joints affected (polyarticular gout)
- Information on previous therapy (see Section 9.8) and its outcomes

### 11.1.2 Demographic data

The following demographic data will be registered at the study selection step:

- Date of birth
- Sex
- Race

# 11.1.3 Measurement of body weight and height

The patient's height (barefooted) will be measured at the screening visit, and the result recorded in the CRF (rounding to the nearest centimeter). Body weight measurements are taken at

CONFIDENTIAL P. 59 of 84

screening visits, Days 5, 15 and 45, follow-up visits for early withdrawal of the patient from the study, and the result is reported to the nearest kilogram.

The body mass index is calculated automatically in the CRF after entering data on the patient's height and body weight.

#### 11.1.4 Collection of medical history data and information on concomitant diseases

Detailed historical data will be collected during the screening period, including information on all current diseases and all significant (in the Investigator's opinion) past diseases, as well as information on tobacco smoking.

## 11.1.5 Evaluation of creatinine, complete blood count parameters, chest X-ray

At Screening, on Days 5, 15, and 45, the follow-up visit for early withdrawal from the study, the following tests are performed at the study site local laboratory:

- Measurement of creatinine level
- Complete blood count with an assessment of the following parameters:
  - Absolute neutrophil count
  - o Total white blood cell count
  - Platelet count.

Creatinine clearance is calculated automatically in CRF using the Cockcroft-Gault formula:

#### For men:

Creatinine clearance 
$$(mL/min) = \frac{(140 - age^a) \times (weight^b) \times 1.0}{0.81 \times \text{serum creatinine (}\mu\text{mol/L)}}$$

#### For women:

Creatinine clearance (mL/min) = 
$$\frac{(140 - age^a) \times (weight^b) \times 0.85}{0.81 \times \text{serum creatinine (}\mu\text{mol/L)}}$$

- a. Age expressed in years.
- b. Weight in kilograms.

Chest X-ray in 2 views is performed at screening if the patient does not have results of chest X-ray in 2 views or fluorography of the chest in 2 views or chest CT performed within 3 months before the expected date of the first injection of the investigational product.

## 11.1.6 Diagnosis of infections (HIV, hepatitis B, hepatitis C)

On Day 1, prior to patient randomization, the investigator will look for symptoms and signs of hepatitis B and C, including a medical history data. If a patient is suspected of having hepatitis B or C, the patient is not randomized.

To diagnose infections (HIV, HBsAg, HCV Ab) in patients, blood samples are taken on Day 1 prior to randomization for the following tests:

- Express tests for the diagnosis of HIV (OraQuick HIV ½), hepatitis B (SD BIOLINE HBsAg) and hepatitis C (OraQuick HCV Ab)
- Tests for HIV, HBsAg, HCV Ab performed at the central laboratory

Rapid tests for the study are provided by the sponsor. The Sponsor may provide analogs of the above rapid tests for the study. Details on how to perform rapid tests and how to handle blood samples to diagnose infections at the central laboratory are provided in the laboratory manual.

CONFIDENTIAL P. 60 of 84

All rapid tests must be negative to randomize patients into the study.

Central laboratory testing for HIV, HBsAg, and HCV Ab is performed for all patients who signed the informed consent, regardless of rapid test results. The results of these tests will be known after administration of the investigational product to the patient(s) or a decision has been made to not to include the patient from the study. If the patient's test result at the central laboratory is positive for an infection, it will be communicated to the patient. Such patients will be referred to a specialist for further examination and treatment. For such patients, information about the identified concomitant infectious disease should be entered in the eCRF in the Concomitant Diseases section.

# 11.1.7 Diagnosis of tuberculosis

On Day 1, prior to the patient's randomization, the investigator will ask the patient all questions from the TB risk assessment questionnaire (Appendix 1). If the response to any of the questions in this questionnaire is yes, the patient will not be randomized.

The results of the chest x-ray in 2 views taken during the screening will be used to assess the patient's eligibility for participation in the study.

Blood sampling for a T-SPOT.TB test will be carried out either at screening, or during the time the patient is in the hospital.

This test will be carried out in a central laboratory. The results of these tests will be known after administration of the investigational product to the patient(s) or a decision has been made to not to include the patient from the study. If the patient's test result at the central laboratory is positive for an infection, it will be communicated to the patient. Such patients will be referred to a specialist (TB specialist) for further examination and treatment. For such patients, information about the identified concomitant infectious disease should be entered in the eCRF in the Concomitant Diseases section. A positive test result will be considered an AE.

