- 17. Chest X-ray in 2 views is performed at screening if the patient does not have results of chest X-ray in 2 views or fluorography of the chest in 2 views or chest CT performed within 3 months before the expected date of the first injection of the investigational product;
- 18. Serious adverse events are recorded from the time of signing the informed consent to participate in the study. Other adverse events are recorded from the time of administration to the patient (the first intake by the patient) of the investigational product.
- 19. In patients receiving RPH-104, the assessment of injection site reactions is carried out 15, 30, 45 minutes (interval ± 5 min) after administration and then in accordance with the table of study procedures. The physician assesses the presence of tenderness, redness, swelling, induration, hemorrhage and itching at the RPH-104 injection site. The patient is assessed for these reactions at each visit. They are recorded as adverse events.
- 20. Voltaren® (diclofenac) and Ortanol® (omeprazole) are dispensed only for patients receiving Voltaren® (diclofenac).
- 21. In the diaries, patients record information about the development of adverse events and changes in concomitant therapy (discontinuation or dose change) or use of new concomitant therapy. Patients receiving Voltaren® (diclofenac) are also given additional diaries to record information about the use of Voltaren® (diclofenac). The diaries are filled in by patients when they are outside the study site.
- 22. Blood sampling for T-SPOT.TB test should be carried out either at screening, or during the time the patient is in the hospital.
- 23. Urine analysis includes: color, transparency, specific gravity, pH level, glucose, protein, ketone bodies, bilirubin, urobilinogen, nitrites. Analysis of urine sediment includes: leukocyte count, erythrocyte count, epithelial cell count with cell type, and bacterial count.
- 24. Information is collected about all previous therapy for the primary disease—gout, information about other prior therapy is collected for a period of 30 days before the start of screening.

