- 25. Patients who do not tolerate pain receive the rescue medication after 2 hours and until Day 45 of the study after the first use of rescue medication Kenalog® (triamcinolone) to intensify therapy. If it is necessary to use the rescue medication, immediately before its use, an unscheduled assessment of pain severity using a visual analogue scale (VAS) and global assessment of efficacy is to be performed and the time of use of the rescue medication is to be registered.
- 26. If patients receiving Voltaren® (diclofenac) miss visits on Day 10, 18 and 22, they record pain intensity in the assessed joint and the patient global assessment of efficacy at home. For this purpose, they are given patient questionnaires to take home at Visits on Days 6 (1 score) and 15 (2 scores).
- 27. By the decision of the investigator, after the use of the investigational products, patients can be hospitalized and remain under observation in the hospital. All procedures in accordance with the visit schedule for these patients are carried out in a hospital setting. Patients who, in the investigator's opinion, are not eligible for hospitalization, are followed up for at least 3 hours after the investigational product administration, after which they can leave the study site and continue to participate in the study with all assessments performed on an outpatient basis.

CONFIDENTIAL P. 22 of 84

- 28. At the visit on Day 1, all patients in the Voltaren® (diclofenac) group are given the drug for dosing at the study site; patients who are hospitalized by the decision of the investigator are given the drug in a hospital setting before being discharged; subsequently, these patients are given the drug in an amount sufficient for self-administration at home in accordance with the study protocol. Patients who are not eligible for hospitalization receive the drug for self-administration on Day 1 after the rest of the procedures and assessments.
- 29. Patients receiving Voltaren® (diclofenac) on an outpatient basis are allowed to leave the study site 3 hours after taking the drug. In this case, they are given patient questionnaires (measurement of pain in the assessed joint, patient global assessment of efficacy) to fill at home 4 and 8 hours after taking the drug.
- 30. New patient diaries are issued as needed.

CONFIDENTIAL P. 23 of 84

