#### 12 ADVERSE EVENTS

In this study, an **adverse event** (AE) means any untoward medical event in a patient receiving the study drug that does not necessarily have a causal relationship with the drug. Thus, an adverse event can be any unintended and untoward symptom (for example, a laboratory abnormality), a symptom or a disease with temporal relationship with the use of the drug, regardless of whether they are considered to be related with the drug.

Clinical signs of treatment failure are not adverse events. For example, persistent pain or swelling in an affected joint should not be reported as an adverse event.

Symptoms, syndromes, and diseases noted prior to the study therapy, but after the patient signed the informed consent form, are recorded in the CRF as Concomitant Diseases.

Laboratory and investigation abnormalities should be registered as adverse events if these abnormalities are regarded by the investigator as clinically significant.

An **adverse drug reaction** is any adverse event with at least a possible (possible, probable, or certain) relationship with the use of the investigational medicinal product.

AE severity is graded according to the CTCAE classification v.5.0.

All adverse events should be monitored until resolution or stabilization (assessed by the investigator).

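### Section 11.1.7 records every positive T-SPOT.TB as both a concomitant disease and an AE, whatever the sample date and with no onset date, so a baseline finding can enter the treatment-emergent tables

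*Combined protocol and SAP*

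**What the plan says.** On timing, Section 11.1.7 states: "Blood sampling for a T-SPOT.TB test will be carried out either at screening, or during the time the patient is in the hospital". Note 22 to Table 3.1 agrees. The table schedules no second test. Note 27 says that "after the use of the investigational products, patients can be hospitalized and remain under observation in the hospital", so the hospital option can mean blood drawn after dosing. Section 11.1.7 also says that the central laboratory result arrives after dosing, or after a decision not to include the patient.

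For a positive result, Section 11.1.7 gives two instructions. The first is that "information about the identified concomitant infectious disease should be entered in the eCRF in the Concomitant Diseases section". The second is "A positive test result will be considered an AE".

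The general rules are these:
- Section 12 sends to Concomitant Diseases "Symptoms, syndromes, and diseases noted prior to the study therapy, but after the patient signed the informed consent form". It makes laboratory abnormalities AEs only where the investigator judges them clinically significant.
- Section 12.1 registers non-serious AEs from the first dose and requires an onset date for each.
- Section 13.6.1 defines treatment-emergent AEs as those occurring from administration to 45 days after it. Its only pre-treatment category is for serious events.

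**The concern.** Blood drawn before dosing can only show the patient's state before dosing. Under Section 11.1.7 such a finding is nevertheless an AE if positive, and it is also entered as a pre-existing disease. The plan does not say whether its onset is the sample date or the result date. If sites use the result date, the finding is tabulated as treatment-emergent.

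Infection is a natural safety question for a drug that binds IL-1β, and the arms are small. A few baseline positives could appear as on-treatment infection-related findings, spread unevenly across doses by chance. With only one test per patient, the tables could not show which positives were new.

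**Working it through.** **1. The rules side by side.**

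| Finding | When obtained | When known | Recorded as |
|---|---|---|---|
| HIV, HBsAg, HCV Ab at the central laboratory (11.1.6) | before randomization | after dosing | Concomitant Diseases only |
| Physical examination abnormality (11.5.3) | before first dose | same visit | Concomitant Diseases |
| Clinically significant ECG abnormality (11.5.5) | screening | before randomization | concomitant disease |
| Other laboratory abnormality (12) | any | any | AE only if clinically significant |
| T-SPOT.TB positive (11.1.7) | screening or hospital stay | after dosing | Concomitant Diseases and AE, unconditionally |

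The closest parallel is the first row. For those infections Section 11.1.6 says: "For such patients, information about the identified concomitant infectious disease should be entered in the eCRF in the Concomitant Diseases section". No AE sentence follows. A T-SPOT.TB drawn at screening has the same timing but a different rule.

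**2. What the dating decides.** Take a sample drawn before dosing with a result after it.
- Onset set to the sample date: the event precedes the start of registration in Section 12.1 and the window in Section 13.6.1, so it is not treatment-emergent.
- Onset set to the result date: it is treatment-emergent if the result arrives within 45 days of dosing.

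The text reviewed does not choose between these.

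**3. Size for one patient.** Planned arms (Section 13.1.2): 15 + 4 × 14 + 14 = 85. One patient is 1/14 = 7.1 points, or 1/15 = 6.7 points in the 4 mg arm. This is the effect on the row for the specific AE term.

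For the any-AE rate, the patient adds something only if he or she has no other AE. In Table 4.2, RPH-104 subjects with any AE number 5 + 3 + 4 + 5 + 5 = 22 of 25, or 88%. If that rate held here (an assumption, since these were healthy volunteers), the average addition would be 7.1 × (1 − 0.88) = 0.9 points.

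**4. How many positives.** The documents give no positivity rate p, so the range below is an assumption. Expected positives in an arm of 14 are 14p. The chance of at least one is 1 − (1 − p)^14. The last column is the binomial probability that two arms of 14 differ by two or more positives by chance.

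| Assumed p | Expected per 14 | At least one in 14 | Two arms differ by 2 or more |
|---|---|---|---|
| 2% | 0.28 | 24.6% | 4.8% |
| 5% | 0.70 | 51.2% | 17.2% |
| 10% | 1.40 | 77.1% | 32.8% |
| 20% | 2.80 | 95.6% | 47.4% |
| 30% | 4.20 | 99.3% | 53.5% |

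These figures count every positive. Those from pre-dose samples are the same number or fewer.

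**5. The interim.** Section 13.7 analyses 47 patients, and Section 4 says that the interim report may become final. Period 1 takes 22, leaving 47 − 22 = 25. If these followed the 2:2:2:2:1 ratio, each higher-dose arm would have 25 × 2/9 = 5.6 patients, and one patient would be 1/5.6 = 18 points on the row for the term. Actual arm sizes are not given.

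**The case against.** The case on the other side is substantial, and much of it stands.

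- **Section 12 is not literally contradicted.** A reader might infer that the AE sentence breaks the rule for pre-treatment conditions. That rule covers what is noted before study therapy, and this result is noted afterwards. The firm inconsistencies are within Section 11.1.7, with Section 11.1.6, and with the clinical-significance condition in Section 12.
- **Inflation is conditional.** A reader might infer that on-treatment AE rates are inflated as a matter of course. That follows only if onset is dated by the result.
- **Nothing is counted twice.** Concomitant diseases and AEs are separate CRF sections, and no planned table adds them.
- **There is no built-in bias against RPH-104.** T-SPOT.TB is not among the RPH-104-only procedures in note 12 to Table 3.1, so diclofenac patients are tested too. The added events balance in expectation, though not reliably in arms this small.
- **Other rules limit the harm.** Exclusion criterion 23 and the Appendix 1 questionnaire may lower the number of positives. Safety analysis is descriptive, and a pre-existing positive can be rated unrelated and so stay out of the related-AE table.
- **The HIV and hepatitis parallel is incomplete.** T-SPOT.TB may be drawn after dosing, so a different rule could be justified for those samples. It remains unexplained for screening samples.
- **The rule may be deliberate caution.** Calling every positive an AE secures a causality rating and AE follow-up. That is a reason to keep pre-dose positives visible, but not to tabulate them as treatment-emergent.

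**Conclusion.** The point holds as a recording and dating defect. One positive T-SPOT.TB gets two classifications regardless of sample date, with no onset date, and the handling differs from that of late HIV and hepatitis results without explanation. With no paired test, a positive cannot be shown to have arisen on treatment, even when the sample is post-dose.

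The consequence is conditional: dated by its result, a baseline finding enters the treatment-emergent tables. One patient is then 7.1 points (6.7 at 4 mg) for the term itself at planned arm sizes, and less on average for the any-AE rate. The total effect is unknown because the number of positives, the split of samples before and after dosing, and site dating practice are not given. The separate statistical analysis plan announced in Section 13.1.7 might supply a rule, but its text is not in the document reviewed.

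The issue is minor. It does not touch the primary endpoint, the sample size or the efficacy analysis.

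**What to change.** In Section 11.1.7 and the separate statistical analysis plan:

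1. Date a positive T-SPOT.TB by its sample date.
2. Record a positive from a pre-dose sample under Concomitant Diseases, keep it out of the treatment-emergent AE tables, and show it in a separate listing.
3. List a positive from a post-dose sample with its sample date and a note that there is no baseline test.
4. Reconcile Sections 11.1.6, 11.1.7, 12, 12.1 and 13.6.1, including whether the clinical-significance condition applies to this test.

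The cost is a few sentences. The 47 interim patients have completed participation, so a protocol change cannot alter how their data were collected. For them the table rule belongs in the analysis plan, which is to be approved before the interim data lock, and it needs the T-SPOT.TB sample date and time in the dataset. The small downside is that pre-dose positives no longer receive an AE causality rating or AE follow-up; the separate listing keeps them visible. Patient notification and referral are unchanged.

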# 11.1.8 Serum Pregnancy Test

Serum pregnancy test for women of childbearing potential will be performed at the study site. Serum pregnancy tests for women of childbearing potential should be performed at screening and at the Day 45 visit or follow-up visit if the patient withdraws from the study early. To enroll a patient in the study, a pregnancy test at screening must be performed after the patient has signed the informed consent from and the result of this test must be negative.

Women are considered postmenopausal and of non-childbearing potential if spontaneous (natural) amenorrhea has lasted at least 24 months with a respective clinical presentation (e.g. appropriate age, history of vasomotor symptoms), or if they underwent bilateral surgical removal of the ovaries (with or without hysterectomy) or tubal ligation at least 6 weeks before the proposed randomization date. In the case of removal of the ovaries only, a woman is of non-childbearing potential only after confirmation of the reproductive status by a hormone test.

# 11.2 Evaluation of pharmacokinetics and anti-drug antibodies

Evaluation of the RPH-104 pharmacokinetics and anti-drug antibodies is carried out only for patients treated with RPH-104.

The time of blood sampling for pharmacokinetics and anti-antibodies is presented in Table 3.1.

Acceptable time windows for blood sampling for pharmacokinetics and anti-antibodies are shown in Table 3.1.

It is essential to record in the CRF the real sampling time for each blood sample and to pay particular attention to labeling of the samples.

CONFIDENTIAL P. 61 of 84

The methods used to collect blood samples, obtain plasma, and store samples are described in the guideline for laboratory tests.

Serum samples for the assessment of pharmacokinetics and anti-drug antibodies are sent to Covance Central Laboratories. The cargo handling procedure is described in the laboratory manual.

